4.4.3 Dose-Adjustment of Study Drug

Throughout the dosing period the following will apply:

- 1) PEX dose may be decreased at any time for suspected elevated PEX levels or related AE.
- 2) Possible PEX dose levels will be:
 - a. Period 1: 35, 70, 105, 140, 175, and 210 mg (tablet strength of 35 mg).
 - b. Period 2: 35, 70, 105, 140, 175, 210, 245, and 280 mg (tablet strength of 35 mg).
- 3) In general, only one dose adjustment should be made per two-week period starting at the end of week 2 in Period 1. If the PI thinks an additional dose adjustment should be made, the PI should contact the Medical Monitor.
- 4) Upon notification of a dose adjustment the site should contact patient as soon as possible to initiate dose adjustment.

- 5) To achieve the higher target range for PEX in Period 2, the dose will initially be adjusted based on the plasma PEX level measured at Week 6 in Period 1. This dose adjustment will be performed at the end of the Week 8 visit (start of Period 2) in accordance with the Period 2 column in Table 4.1. **Important:** Any change made at Week 6 will need to be accounted for when adjusting the dose at Week 8.
- 6) Dose adjustments will proceed based on the following criteria (see Table 4.1):

Table 4.1 Possible dose-adjustments in Periods 1 and 2

Systemic Perhexiline Levels (PEX) (ng/mL)**	Period 1 (Weeks 2 – 8)	Period 2 (Weeks 9 – 16)
	Target Range 100-300 ng/mL Start Dose of 70 mg/day, 2 tablets/day (tablets to be taken orally in the evening) Maximum Dose 210 mg (6 tablets)	Target Range 300-500 ng/mL Start dose will be the dose-adjustment decision based on the Period 1, Week 6 level of PEX† (tablets to be taken orally in the evening) Maximum Dose 280 mg (8 tablets)
< 50	+2 tablets per day#	+2 tablets per day#
50 to 100	+1 tablet per day#	+2 tablets per day#
101 to 200	No change	+1 tablet per day#
201 – 300	No change	+1 tablet per day#
301 – 400	-1 tablet per day*	No change
401 – 500	-2 tablets per day*	No change
501 – 600	-3 tablets per day*	-1 tablet per day*
601 – 700	Discontinue for 1 day, and -3 tablets per day*	Discontinue for 1 day, and -2 tablets per day*
701 - 900	Discontinue for 3 days, and -4 tablets per day*	Discontinue for 1 day, and -3 tablets per day*
901 - 1200	Discontinue for 7 days, and -5 tablets per day*	Discontinue for 3 days, and -4 tablets per day*
> 1200	Discontinue for 7 days, and -5 tablets per day*	Discontinue for 7 days, and -5 tablets per day*

Unless the patient has already reached the highest daily dose permitted of six (6) tablets or 210 mg in Period 1 and eight (8) tablets or 280 mg in Period 2

* The lowest daily dose is one (1) tablet per day or 35 mg.

** Blood sampling for plasma PEX, CIS and TRANS measurement should be obtained approximately 12 hours following dosing on the previous day.

† Any change made at Week 6 will need to be accounted for when adjusting the dose at Week 8.

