4. Upon notification of a dose adjustment the site should contact the patient as soon as possible to initiate dose adjustment according to Table 1.1, below.
5. To achieve the higher target range for PEX in Period 2, the dose will initially be adjusted based on the plasma PEX level measured at Week 6 in Period 1. This dose adjustment will be performed at the Week 8 visit (start of Period 2) in accordance with the Period 2 column in Table 1.1, below. **Important:** Any change made at Week 6 will need to be accounted for when adjusting the dose at Week 8.

Table 1.1 Dose-adjustments from Week 2, Period 1 and throughout Period 2

Systemic Perhexiline Level (PEX) (ng/mL)**	Period 1 (Weeks 2 – 8) Target Range 100-300 ng/mL Start Dose of 70 mg/day, 2 tablets per day (Tablets to be taken orally in the evening) Maximum Dose 210 mg (6 tablets)	Period 2 (Weeks 9 – 16) Target Range 300-500 ng/mL Start dose will be the dose-adjustment decision based on the Period 1, Week 6 level of PEX† (Tablets to be taken orally in the evening) Maximum Dose 280 mg (8 tablets)
< 50	+2 tablets per day#	+2 tablets per day#
50 to 100	+1 tablet per day#	+2 tablets per day#
101 to 200	No change	+1 tablet per day#
201 – 300	No change	+1 tablet per day#
301 – 400	-1 tablet per day*	No change
401 – 500	-2 tablets per day*	No change
501 – 600	-3 tablets per day*	-1 tablet per day*
601 – 700	Discontinue for 1 day, and -3 tablets per day*	Discontinue for 1 day, and -2 tablets per day*

	701 - 900	Discontinue for 3 days , and -4 tablets per day*	Discontinue for 1 day , and -3 tablets per day*
	901 - 1200	Discontinue for 7 days , and -5 tablets per day*	Discontinue for 3 days , and -4 tablets per day*
	> 1200	Discontinue for 7 days , and -5 tablets per day*	Discontinue for 7 days , and -5 tablets per day*

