	
# Unless the patient has already reached the highest daily dose of six (6) tablets or 210 mg in Period 1 and eight (8) tablets or 280 mg in Period 2
 
* The lowest daily dose is one (1) tablet per day or 35 mg.
 
** Blood sampling for plasma PEX, CIS and TRANS measurement should be obtained approximately 12 hours following dosing on the previous day. Results for systemic PEX and CIS levels will be reported to the study sites.
 
† Any change made at Week 6 will need to be accounted for when adjusting the dose at Week 8.
 
6. Dose adjustment for QTcF/JTcF prolongation (regardless of PEX levels reported, unless the PEX levels and dose adjustment algorithm result in a dose reduction or discontinuation of a greater magnitude) will proceed as follows for EITHER:
 
a. Patients with a QRS interval \leq 100 msec WITH;
 
 • A prolonged QTcF > 540 msec OR, • An increase in QTcF > 75 msec over baseline AND QTcF > 500 msec 
b. Patients with a baseline OR any on-study QRS interval > 100 msec WITH:
 
 • An increase in the JTcF > 75 msec over baseline AND the JTcF > 410 msec OR • An on-study JTcF interval > 450 msec 
The dose of study drug will be stopped for 2 days and the daily dose subsequently reduced by 35 mg (for patients receiving \leq 105 mg) or 70 mg (for patients receiving \geq 140 mg) and restarted only if the QTcF/JTcF measurement has fallen back into the acceptable range for continued dosing. If the QTcF/JTcF measurement has NOT fallen back into the acceptable range after stopping drug for 2 days, the process of holding study drug and rechecking the ECG every 2 to 3 days will continue until the QTcF or JTcF limits are not exceeded and at which time study drug may be restarted at the reduced dose. The dose of study drug will not be increased any further during either Period 1 or Period 2 if a dose reduction for QTcF or JTcF prolongation is required.
		

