Subsequent blood samples will be obtained and plasma levels of PEX, CIS and TRANS determined at the end (± 3 days) of every second week (weeks 4, 6, and 8 in Period 1, and weeks 10, 12 and 14 in Period 2); the sampling timepoint will be scheduled at approximately 12h after dosing on the previous study day. The analytical results will be available within 3-5 calendar days of the blood sampling and results for PEX and CIS will be reported to the study sites. These will be used to guide dose adjustment according to Table 4.1 below and to evaluate the CIS:PEX ratio. At the conclusion (± 3 days) of Period 2 (end of Week 16), an additional blood sample will be obtained at approximately 12h after dosing on the previous study day and plasma levels of PEX, CIS and TRANS determined. A final blood sample will be obtained at the conclusion of the 4-week safety follow-up period (end of week 20) and plasma levels of PEX, CIS and TRANS determined.

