4.4.4 Dose-Adjustment for QTcF/JTcF Prolongation

Any dose adjustment instructions due to QTcF/JTcF prolongation will be at the direction of the ECG Core laboratory. Decisions to hold dosing until ECG Core Laboratory analysis is complete may be made at the site.

Dose adjustment for QTcF/JTcF prolongation (regardless of systemic PEX levels, unless the PEX levels and dose adjustment algorithm result in a dose reduction or discontinuation of a greater magnitude) will be done as described below for:

- a. Patients with a QRS interval \leq 100 msec WITH;
 - A prolonged QTcF $>$ 540 msec OR,
 - An increase in QTcF $>$ 75 msec over baseline AND QTcF $>$ 500 msec
- b. Whenever either the baseline or a subsequent ECG has a prolonged QRS $>$ 100 msec, changes in the JTcF will be used for all further dose-adjustment decisions throughout the remainder of the study for those patients. In a patient with a baseline or an on-study ECG showing a QRS interval $>$ 100 msec, the dose will be adjusted as described below IF;
 - The change from baseline in JTcF is $>$ 75 msec over baseline AND the JTcF interval is $>$ 410 msec OR,
 - An on-study JTcF interval is $>$ 450 msec

The dose of study drug for such patients will be stopped for 2 days and the daily dose subsequently reduced by 35 mg (for patients receiving \leq 105 mg) or 70 mg (for patients receiving \geq 140 mg) and restarted only if the QTcF/JTcF measurement has fallen back into the acceptable range for continued dosing. If the QTcF/JTcF measurement has NOT fallen back into the acceptable range after stopping drug for 2 days, the process of holding study drug and rechecking the ECG every 2 to 3 days will continue until the QTcF or JTcF limits are not exceeded and at which time study drug may be restarted at the reduced dose. The dose of study drug will not be increased any further during the remainder of the study (neither Period 1 or Period 2) if a dose reduction for QTcF or JTcF prolongation is required.

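### The Period 2 dose increase can start on the evening of Week 8, before that day's ECG has been centrally read; a 48h read gate would close this small gap cheaply

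*Protocol*

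**What the plan says.** **Timing of the step.** Protocol 4.4.3 item 5 takes the Week 6 PEX level and states: "This dose adjustment will be performed at the end of the Week 8 visit (start of Period 2". Synopsis item 5 agrees: "This dose adjustment will be performed at the Week 8 visit (start of Period 2". Neither attaches an ECG condition. Both add: "Any change made at Week 6 will need to be accounted for when adjusting the dose at Week 8".

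**Other level-driven changes.** These wait for a new assay result (4.4.2): "The analytical results will be available within 3-5 calendar days of the blood sampling".

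**QT rule.** Under 4.4.4, "Any dose adjustment instructions due to QTcF/JTcF prolongation will be at the direction of the ECG Core laboratory". Sites are allowed, but not obliged, to hold dosing while a read is pending. The rule applies "regardless of systemic PEX levels, unless the PEX levels and dose adjustment algorithm result in a dose reduction or discontinuation of a greater magnitude". Once a QT reduction is required, "The dose of study drug will not be increased any further during the remainder of the study". The size of the cut is given in 4.4.4 and in synopsis item 6: "The dose of study drug will be stopped for 2 days and the daily dose subsequently reduced by 35 mg" for patients receiving 105 mg or less, and 70 mg for those receiving 140 mg or more. Dosing restarts only when QTcF or JTcF is back in range.

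**Read time.** The 48h maximum (Table 6.2 footnote R; 6.4) and the rule that no drug is dispensed before central confirmation (Table 6.2 footnote E; 6.4) concern the Baseline ECG. Neither document gives a read time for on-study ECGs.

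**The concern.** Week 8 is the one scheduled dose step that uses a result already in hand. Section 6.1 starts visit procedures in the morning and 4.4.1 puts dosing in the evening, so the first raised dose can follow the Week 8 ECG by hours. The bar on increases in 4.4.4 protects the patient only once the exceedance is known.

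Protocol 2.5 names QT prolongation as a reason for enhanced monitoring. Yet the plan requires a central read before the first 70 mg dose and none before the planned move to a higher exposure range. A patient who first crosses a QT limit at Week 8 could take raised doses until the read arrives. If the later cut is counted from the raised dose, that patient could restart at the dose on which the limit was crossed.

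**Working it through.** The plan states no figure to reproduce here. The check is a timeline followed by dose arithmetic.

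**1. Timeline at Week 8**
- Morning: triplicate ECG, taken before CPEX and blood draws (6.6, 6.7).
- End of visit: dose raised from the Week 6 level (4.4.3 item 5).
- Evening: first raised dose (4.4.1).
- Core Laboratory read: no time stated. If it took 48h, as allowed at Baseline, raised doses could be taken on the visit evening and the next evening, so two doses.

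**2. Who is exposed**
- Table 4.1, Period 2 column: +2 tablets up to 100 ng/mL, +1 tablet at 101-300, no change at 301-500. The tablet is 35 mg.
- Table 4.1, Period 1 column at 101-300: no change. Unless the dose was altered for another reason, these patients had their Week 6 ECG on the same dose, with about two weeks for it to be read.
- A patient with an earlier QT reduction is barred from the increase, so only a first exceedance at Week 8 matters.
- The limits are high: QTcF above 540 msec, or above 500 with a rise over 75; with QRS above 100 msec, JTcF above 450, or above 410 with a rise over 75.

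**3. Concentration effect** (thorough QT study, Protocol 2.5)

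Slope = (22.8 − 15.3) / (677.9 − 278.6) = 7.5 / 399.3 = 0.0188 msec per ng/mL, about 1.9 msec per 100 ng/mL. This is a mean across subjects and does not describe a patient already past a limit.

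**4. Which dose the QT cut is counted from**

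cut(x) = x − 35 if x ≤ 105, otherwise x − 70, with a minimum of 35 mg. The minimum comes from the Table 4.1 footnote; 4.4.4 does not repeat it, so it is assumed. For the usual +1 tablet step (Week 6 level 101-300 ng/mL):

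| Dose at Week 8 ECG (mg) | Raised dose (mg) | Restart, cut from raised dose (mg) | Restart, cut from ECG dose (mg) |
|---|---|---|---|
| 35 | 70 | 35 | 35 |
| 70 | 105 | 70 | 35 |
| 105 | 140 | 70 | 70 |
| 140 | 175 | 105 | 70 |
| 175 | 210 | 140 | 105 |
| 210 | 245 | 175 | 140 |

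The two readings differ by 35 mg at 70, 140, 175 and 210 mg. They decide whether there is any reduction only at 70 mg. At 35 mg the minimum prevents a reduction on either reading.

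**5. Cost of waiting**

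At most about 2 days of an 8-week period: 2/56 = 3.6%.

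**The case against.** The plan does address a pending read: it leaves the hold to the site, which can be defended as a choice. The ECG is the first procedure of the visit, and SAP 3.2.5 makes traces available to the investigator, though without a time. Three on-study ECGs come before Week 8, and the typical on-target patient has already been read on the same dose. An on-study turnaround may exist in Core Laboratory documents that are not part of this plan. The remark that other visits leave time for a read during the 3-5 day assay wait is itself an assumption, because no read time is given. All of this stands, and it makes the exposure small. It does not put an ECG condition on the Week 8 step.

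A reader might infer three stronger things that the documents do not support.

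- *Most patients would restart at the dose that crossed the limit.* Take Week 6 levels up to 300 ng/mL (six doses by three bands, 18 combinations) and count the cut from the raised dose. Then 14 of 18 restart at the ECG dose, but only if the full Period 2 step is added on top of any Week 6 change. That fits poorly with the instruction to account for that change. If the Period 2 column is applied to the dose before the Week 6 change, 14 of 18 combinations rise and 5 of those 14 restart at the ECG dose, one of them at the 35 mg minimum. These count rules, not patients.
- *A patient could restart above the ECG dose (35 to 105, then 70 mg).* A +2 step needs a Week 6 level of 100 ng/mL or less, and Table 4.1 would already have raised a 35 mg patient at Week 6. The path is not reached if the table is followed.
- *A QT cut should be added to a PEX cut already made.* Section 4.4.4 lets the reduction of greater magnitude govern, which points to the larger cut and not the sum.

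**Conclusion.** The sequencing gap is real and small. As written, the Period 2 increase can take effect on the evening of Week 8 with that day's ECG unread, and nothing mandatory in either document prevents it. The gap matters only for a first exceedance at Week 8. The mean concentration effect is modest, and 4.4.4 overrides the increase once the exceedance is known. The documents give no frequency for such an exceedance, so no claim of likely harm is made.

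The unclear reference dose is a secondary point. 'Receiving' reads most naturally as the current, raised dose, which gives the smaller net cut. On the usual step this removes the reduction altogether only for a patient on 70 mg at the ECG.

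The conclusion assumes that sites follow the stated timing literally and that no on-study read time is set elsewhere. It is a cheap improvement, optional, and justified by its low cost.

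**What to change.** **Main change (4.4.3 item 5 and synopsis item 5).** Make the Week 8 increase only after the Core Laboratory confirms that the Week 8 ECG is within the 4.4.4 limits, with a maximum read time of 48h as at Baseline. Until then the patient stays on the Period 1 dose, and is told of the change by contact under 6.10.

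*Cost:* escalation may start up to about 2 days later (3.6% of Period 2), and the Core Laboratory must read up to about 33 Week 8 ECGs within 48h. No visit is added, because drug is already dispensed at Week 8 (Table 6.2 footnote Q).

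**Minor change (4.4.4 and synopsis item 6).** When the dose has been raised since the qualifying ECG, count the QT reduction from the dose in force at that ECG, with a 35 mg minimum. When a PEX-driven cut has already been made, keep the greater-magnitude rule: the lower of the two resulting doses applies and the cuts are not added. For example, with the ECG at 210 mg and a PEX cut since to 175 mg, the QT rule gives 210 − 70 = 140 mg. The lower of 140 and 175 is 140 mg, so restart is at 140 mg and not at 175 − 70 = 105 mg.

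*Cost:* one or two sentences in the same amendment. It would also cover increases made at other visits before a read arrives.

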4.4.4 Dose-Adjustment for QTcF/JTcF Prolongation

Any dose adjustment instructions due to QTcF/JTcF prolongation will be at the direction of the ECG Core laboratory. Decisions to hold dosing until ECG Core Laboratory analysis is complete may be made at the site.

Dose adjustment for QTcF/JTcF prolongation (regardless of systemic PEX levels, unless the PEX levels and dose adjustment algorithm result in a dose reduction or discontinuation of a greater magnitude) will be done as described below for:

- a. Patients with a QRS interval \leq 100 msec WITH;
 - A prolonged QTcF $>$ 540 msec OR,
 - An increase in QTcF $>$ 75 msec over baseline AND QTcF $>$ 500 msec
- b. Whenever either the baseline or a subsequent ECG has a prolonged QRS $>$ 100 msec, changes in the JTcF will be used for all further dose-adjustment decisions throughout the remainder of the study for those patients. In a patient with a baseline or an on-study ECG showing a QRS interval $>$ 100 msec, the dose will be adjusted as described below IF;
 - The change from baseline in JTcF is $>$ 75 msec over baseline AND the JTcF interval is $>$ 410 msec OR,
 - An on-study JTcF interval is $>$ 450 msec

The dose of study drug for such patients will be stopped for 2 days and the daily dose subsequently reduced by 35 mg (for patients receiving \leq 105 mg) or 70 mg (for patients receiving \geq 140 mg) and restarted only if the QTcF/JTcF measurement has fallen back into the acceptable range for continued dosing. If the QTcF/JTcF measurement has NOT fallen back into the acceptable range after stopping drug for 2 days, the process of holding study drug and rechecking the ECG every 2 to 3 days will continue until the QTcF or JTcF limits are not exceeded and at which time study drug may be restarted at the reduced dose. The dose of study drug will not be increased any further during the remainder of the study (neither Period 1 or Period 2) if a dose reduction for QTcF or JTcF prolongation is required.

4.5 MANAGEMENT OF POSSIBLE PEX OVERDOSAGE

For the purpose of this study an overdose is defined when there is a systemic level of PEX $>$ 1,200 ng/ml at any timepoint. Suspected overdose associated with lower PEX systemic levels should also be reported as an AE or SAE if warranted by the clinical history and/or laboratory findings. Alternative explanations, such as a change in medications that may alter the patient's CYP2D6 metabolism, should be considered.

Reported symptoms following overdosage are nausea and vomiting. Other symptoms that have not been reported but would be anticipated are ataxia and headache. Hepatic damage and cardiac arrhythmias may possibly occur [Pexsig Product Information 2000].

Treatment should be symptomatic and supportive. PEX overdose should result in careful monitoring of drug levels, continuous cardiac monitoring and serial blood glucose recordings in diabetic patients. In patients who are not fully conscious or have impaired gag reflex, consideration should be given to administering activated charcoal via a nasogastric tube, once the airway is protected. Adequate urinary output should also be maintained.

Dialysis is not indicated because of the high degree of protein and tissue binding.

4.6 PATIENT WITHDRAWAL AND DISCONTINUATION

Patients have the right to withdraw from the study at any time without needing to give any reason. Should a patient withdraw, all efforts should be made to complete and report observations prior to withdrawal as thoroughly as possible. Patients who choose to discontinue from the study will not be replaced.

The Investigator may withdraw patients in the event of intercurrent illness, AEs, protocol violations, administrative or other reasons. The Investigator is strongly encouraged to contact the Medical Monitor prior to discontinuation of study drug or withdrawal of patient from the study.

Discontinuation of PEX or discontinuation from the study is **mandatory** for:

- Patients whose baseline VO₂MAX is more than ±20% of their screening VO₂MAX, *i.e.*;
(*BASELINE VO₂MAX* – *SCREEN VO₂MAX*)/ *SCREEN VO₂MAX* > ±20%
- Patients who are unable or unwilling to return to the study site to repeat a CPEX test that did not meet the prospectively defined acceptance criteria as determined by the centralized CPEX assessor
- Patients identified as PMs of PEX at the week 1 (day 8) study visit. Despite the screening genotyping, which is 95-97% effective at identifying PMs, there may be a limited number of phenotypic PMs. Phenotypic PM subjects will be identified by determination of the PEX metabolic ratio (MR). This MR is the ratio of CIS to the parent compound, PEX. If the CIS:PEX is <0.4, the patient will be deemed a phenotypic PM regardless of genotype. These patients are at risk for clinically significant elevated plasma PEX levels. Such elevated plasma levels could decrease tolerability or increase the risk of short, self-limited toxicity; if unchecked longer term toxicities could result. Hence, as with the genotypic PMs, these phenotypic PM subjects will be withdrawn from the study. (Patients with a CIS:PEX ratio <0.4 after the week 1 visit will not automatically be withdrawn from the study. These patients should be further evaluated and the patient status will be discussed with the Medical Monitor.)
- Patients with persistent elevations in ALT or AST; see Appendix C for the definition of “persistent”
- Female study participants discovered to be pregnant during the treatment period

Discontinuation of PEX should be considered in the following situations [Phan *et al.*, 2009a] following discussion with the Medical Monitor:

- Appearance of new onset or exacerbation of peripheral neuropathy. However, discontinuation for peripheral neuropathy should only be done after consultation with the Medical Monitor.
- Persistent or marked hypoglycemia that is unresponsive to therapeutic modification (such as reduction of dose of insulin or oral hypoglycemic agent)
- Excessive weight loss
- Hospitalization for newly diagnosed ventricular tachycardia, or ventricular fibrillation

